ECG, ECHO/MUGA ^d	Same as baseline	Same as baseline

- a. If a patient does not meet the requirements for treatment continuation on Day 1 of the following cycle, the infusion of study drugs will be withheld until recovery or for a maximum of 14 days. After this period, if delay is due to toxicity assessed as related to study drug, a dose decrease of 20% is mandatory; up to a maximum of two individual dose reductions are allowed. Patients needing additional dose reductions must be withdrawn from the trial.
- b. If a patient does not meet the requirements for treatment continuation on Day 15, the administration of plitidepsin will be omitted. Patients requiring frequent dose omissions may have a dose reduction of 20% upon Investigator and Sponsor agreement. In no case more than two dose reductions are allowed
- c. Any grade accepted for increased GGT and/or AP, and up to grade 2 peripheral neuropathy.
- d. To be performed every three months unless more frequent assessments are clinically indicated.

AEs: adverse event(s); ANC: absolute neutrophil count; AP: alkaline phosphatase; BM: bone marrow; AST/ALT: aspartate aminotransferase/alanine aminotransferase; CPK: creatine phosphokinase; GGT: γ-glutamyltranspeptidase; ECG: electrocardiogram; ECHO/MUGA: echocardiogram/multiple-gated acquisition scan.

7.4 **DOSE REDUCTION CRITERIA**

Patients experiencing frequent dose omissions and/or unacceptable toxicity, defined as

- less than 50% compliance with treatment schedule, and/or
- grade \geq 3 febrile neutropenia, or
- grade 4 neutropenia and infection, or
- grade 4 neutropenia lasting > 7 days (except for patients with extensive BM involvement), and/or
- grade 4 thrombocytopenia (except for patients with extensive BM involvement), and/or
- grade 4 thrombocytopenia with grade ≥ 3 bleeding (in patients with extensive BM involvement), and/or
- any grade ≥ 3 clinically relevant non-hematological toxicity other than non-optimally treated nausea and vomiting, diarrhea lasting < 48 hours and/or grade ≥ 3 asthenia/fatigue lasting < 5 days

may continue treatment after reducing 20% of the dose of plitidepsin (first reduction to 4 mg/m^2 , and second reduction to 3.2 mg/m^2), upon Sponsor agreement, if patient benefit is perceived.

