8.2 Treatment administration

Total cumulative dose, time on treatment, dose intensity and relative dose intensity, cycle delay, and dose reductions will be described following standard tables detailed in Appendix I.

Total cumulative dose by drug, expressed in mg/m² for plitidepsin, or in mg of dexamethasone, is the sum of all the product doses from the first cycle until last cycle including the dose received in last cycle.

Patients will be considered to be on-treatment for the duration of their treatment and 30 days following the last treatment dose. Those patients in the control arm (Arm B) who crossed over to the combination arm (Arm A) after disease progression will be considered on-treatment for the duration of their whole treatment (dexamethasone alone + dexamethasone in combination with plitidepsin) and during the first 30 days following the last treatment dose. If the patient starts any new antitumor therapy outside this clinical trial or dies within 30 days of last treatment dose, the date of administration of this new therapy or the date of death will be considered the date of treatment discontinuation.

However, as a convention, for dose intensity calculation purposes, the duration of the last cycle is considered to be 28 days. If the patient starts any new antitumor therapy outside this clinical trial or dies within 28 days of last cycle initiation this will be taken into account for the calculation of the duration of the last cycle.

Intended dose intensity is the planned dose per cycle divided by the planned number of weeks by cycle (2.5mg/m²/wk for plitidepsin, 40mg/wk for dexamethasone).

Absolute dose intensity is the actual cumulative dose divided by the number of weeks of treatment. Relative dose intensity (%) is the ratio of absolute dose intensity divided by the intended dose intensity.

The item «Infusion delayed/ omitted: yes/no» in the case report form (CRF) will be used to calculate the delay (on day 1 infusion) or skipped infusions (on day 15 infusion). For cycles considered as delayed by the investigator, the delay will be calculated as:

Delay: Date of current drug administration – Date of previous drug administration – 28.

The first infusion of the first cycle will be excluded from all cycle delay and cycle modification calculations.

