12.1.2 Cycle delays

12.1.2.1 Number of patients and cycles with dosing delay, any relationship

Listing 12.1.2.1.1 Delays

Arm	Patient id.	Cycle	Day	Agent	Previous cycle	Previous cycle start date	Delayed cycle start date	Dose Delay calculated. (days)	Reason for dose delay	Dose Delay Spec.
...										

Results after crossover will be highlighted

Table 12.1.2.1.2 Number of patients and cycles with dosing delay, any relationship

	Arm A		Arm B		Total	
	N	%	N	%	N	%
No. of patients treated						
No. of patients with any dose delay						
No. of cycles administered						
No. of cycles susceptible to be delayed*						
No. of cycles with dosing delay**						
No. of patients with						
No cycles delayed						
1 cycle delayed						
2 cycles delayed						
≥ 3 cycles delayed						

(*) All cycles excluding first cycle. (**) Denominator= Number of cycles susceptible to be delayed

Cycles after crossover will be excluded

Table 12.1.2.1.3 Number of patients and cycles with dosing delay according to the relationship

	Arm A				Arm B			
	Treatment-related**		Non-treatment-related		Treatment-related**		Non-treatment-related	
	N	%	N	%	N	%	N	%
No. of patients with 1 cycle delayed 2 cycles delayed ≥ 3 cycles delayed								
No. of cycles with dosing delay*								

(*) Denominator= Number of cycles susceptible to be delayed. (**)Hematological reason, non-hematological reason or both

Cycles after crossover will be excluded

Table 12.1.2.1.4 Length of dosing delay.

		Arm A						Arm B					
		Treatment-related**		Non-treatment-related		Total		Treatment-related**		Non-treatment-related		Total	
Length of delay	Median (range)	N	%	N	%	N	%	N	%	N	%	N	%
Length of delay ≤ 7 days													
>7 days and ≤14 days													
> 14 days													

(*) Denominator= Number of cycles susceptible to be delayed. (**)Hematological reason, Non-hematological reason or both

Cycles after crossover will be excluded

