12.1.3 Dose omissions

Listing 12.1.3.1.1 Dose omissions

Arm	Patient id.	Cycle	Day	Agent omitted	Cycle start date	Reason for dose omission	Dose omission Spec.
...							

Results after crossover will be highlighted

Table 12.1.3.1.2 Number of patients and cycles with dose omitted, any relationship

	Arm A		Arm B		Total	
	N	%	N	%	N	%
No. of patients treated	X	XX.X	X	XX.X	X	XX.X
No. of patients with any dose omitted						
No. of patients with:						
No plitidepsin omissions			NA			
1 cycle with plitidepsin dose omitted						
2 cycles with plitidepsin dose omitted						
≥ 3 cycles with plitidepsin dose omitted						
No. of patients with:						
No dexamethasone omission						
1 cycle with dexamethasone dose omitted						
2 cycles with dexamethasone dose omitted						
≥ 3 cycles with dexamethasone dose omitted						
No. of cycles administered						
No. of cycles susceptible to have any dose omitted*						
No. of cycles with plitidepsin dosing omitted**			NA			
No. of cycles with dexamethasone dosing omitted**						
No. of cycles with plitidepsin dosing omitted (treatment-related)			NA			
No. of cycles with dexamethasone dosing omitted (treatment-related)						

(*) All cycles excluding first cycle. (**) Denominator= Number of cycles susceptible to have a dose omission
 NA: Not applicable. Cycles after crossover will be excluded

Table 12.1.3.1.3 Number of cycles with treatment-related dose omission by patient

	Arm A		Arm B		Total	
	N	%	N	%	N	%
No. of patients with:	X	XX.X	X	XX.X	X	XX.X
No omission						
1 cycle with treatment-related plitidepsin dose omitted			NA			
2 cycles with treatment-related plitidepsin dose omitted						
≥ 3 cycles with treatment-related plitidepsin dose omitted						
No. of patients with:						
No omission						
1 cycle with treatment-related dexamethasone dose omitted						
2 cycles with treatment-related dexamethasone dose omitted						
≥ 3 cycles with treatment-related dexamethasone dose omitted						

Denominator= Number of patients that were on treatment on day 14 of cycle 1.
 NA: Not applicable. Cycles after crossover will be excluded

Table 12.1.3.1.4 Reasons for dose omissions

Reasons for omissions	Arm A		Arm B		Total	
	N	%	N	%	N	%
Plitidepsin						
Treatment-related	X	XX.X	NA		X	XX.X
Hematological						
Non-hematological						
Both						
Non-treatment-related						
Dexamethasone						
Treatment-related	X	XX.X	X	XX.X	X	XX.X
Hematological						
Non-hematological						
Both						
Non-treatment-related						

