12.1.4 Dose reductions

All dose reductions should be considered and described, specifying the reason for reduction (hematological toxicity, non-hematological toxicity or other causes).

Listing 12.1.4.1.1 Dose reductions

Arm	Patient id.	Cycle	Day	Agent reduced	Cycle start date	Previous dose	Reduced dose	Reason for dose reduction	Dose reduction Spec.
...									

Results after crossover will be highlighted

Table 12.1.4.2 Number of patients and cycles with dose reduction, any relationship

	Arm A		Arm B		Total	
	N	%	N	%	N	%
No. of patients treated	X	XX.X	X	XX.X	X	XX.X
No. of patients with any dose reduced						
No. of patients with:			NA			
No plitidepsin reduction						
1 cycle with plitidepsin dose reduced						
2 cycles with plitidepsin dose reduced						
No. of patients with:						
No dexamethasone reduction						
1 cycle with dexamethasone dose reduced						
2 cycles with dexamethasone dose reduced						
No. of cycles administered						
No. of cycles susceptible to have any dose reduced*						
No. of cycles with plitidepsin dose reduced **			NA			
No. of cycles with dexamethasone dose reduced**						
No. of cycles with plitidepsin dose reduced (Treatment-related)			NA			
No. of cycles with dexamethasone dose reduced (Treatment-related)						

(*) All cycles excluding first cycle of those patients who have only received the first infusion. (**) Denominator= Number of cycles susceptible to have a dose omission

NA: Not applicable. Cycles after crossover will be excluded

Table 12.1.4.3 Number of patients and cycles with dose reduction according to the relationship

Reasons for reductions	Arm A		Arm B		Total	
	N	%	N	%	N	%
Plitidepsin						
No. of cycles with dose reductions*			NA			
Treatment-related	X	XX.X			X	XX.X
Hematological						
Non-hematological						
Both						
Non-treatment-related						
Dexamethasone						
No. of cycles with dose reductions*						
Treatment-related	X	XX.X	X	XX.X	X	XX.X
Hematological						
Non-hematological						
Both						
Non-treatment-related						

(*) Denominator= Number of cycles susceptible to have a dose omission. (**)Hematological reason, non-hematological reason or both.

NA: Not applicable. Cycles after crossover will be excluded

Listing 12.1.4.4 Dose reductions due to AEs

Arm	Patient id.	Cycle	Preferred term code	Adverse event reported (verbatim)	Grade	Relationship	Onset date	Resolved date	Significant consequences
...									

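### The cycle-level dose-omission rate in SAP Table 12.1.3.1.2 drops all of Cycle 1 from its denominator although Cycle 1 doses can be omitted, and the reduction tables point to that same count against their own definition

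*SAP*

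**What the plan says.** Three sets of tables in SAP 12.1 report cycle-level percentages, and each has its own rule for which cycles count.

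- **Delays, Table 12.1.2.1.2:** "All cycles excluding first cycle. () Denominator= Number of cycles susceptible to be delayed".
- **Omissions, Table 12.1.3.1.2:** "All cycles excluding first cycle. () Denominator= Number of cycles susceptible to have a dose omission". The exclusion repeats the delay wording.
- **Omissions, Table 12.1.3.1.3 (patients by number of cycles with a treatment-related omission):** "Denominator= Number of patients that were on treatment on day 14 of cycle 1".
- **Reductions, Table 12.1.4.2, row for susceptible cycles:** "All cycles excluding first cycle of those patients who have only received the first infusion".
- **Reductions, rates in Tables 12.1.4.2 and 12.1.4.3:** "Denominator= Number of cycles susceptible to have a dose omission".

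The general rule in SAP 8.2 is narrower than the omission footnote: "The first infusion of the first cycle will be excluded from all cycle delay and cycle modification calculations". The same section ties the CRF item to "delay (on day 1 infusion) or skipped infusions (on day 15 infusion", that is, delays to Day 1 and skipped infusions to Day 15. Listing 12.1.3.2 counts AE-related omissions on Days 8, 15 and 22. Protocol 7.3 (Table 6, footnote b) does not restrict the omission rule to later cycles: "If a patient does not meet the requirements for treatment continuation on Day 15, the administration of plitidepsin will be omitted".

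**The concern.** Every patient who continues past Day 1 of Cycle 1 has later doses in that cycle that can be missed: plitidepsin on Day 15, and dexamethasone on Days 8, 15 and 22. A denominator without Cycle 1 therefore leaves out cycles that are at risk. The SAP sets no matching rule for the numerator. A patient with one cycle and one omission could add one event and no cycles.

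The reduction tables inherit the problem through a cross-reference. Table 12.1.4.2 counts one set of cycles and then names another as the base of its percentages, so a programmer who follows the footnote literally will divide by the wrong count.

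At stake is how the cycle-level tolerability percentages are read. Comparing safety between arms is a secondary objective, and Cycle 1 makes up a larger share of all cycles in whichever arm has fewer cycles per patient.

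**Working it through.** **No figure to reproduce.** The SAP tables are empty shells and state no omission or reduction rate. The check compares the rules and then works out what each reading would do.

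**Step 1: is Cycle 1 at risk?**

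| Source | Treatment of Cycle 1 |
|---|---|
| SAP 8.2 | Only the first infusion removed |
| Listing 12.1.3.2 | Days 8, 15 and 22, no cycle excluded |
| Table 12.1.3.1.3 | At risk from day 14 of Cycle 1 |
| Table 12.1.4.2, susceptible row | Kept, except for patients with the first infusion only |
| Table 12.1.3.1.2 | Whole cycle removed |
| Tables 12.1.4.2 and 12.1.4.3, rates | Whole cycle removed, through the reference to the omission count |

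The last two rows disagree with the other four.

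**Step 2: reading 1, Cycle 1 events counted in the numerator.** Let N be patients, m mean cycles per patient and r the true rate per cycle. Events are N·m·r and the stated denominator is N·(m-1), so reported/true = m/(m-1). The value of m is not in the documents; the range is an assumption.

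| m | 2 | 3 | 4 | 6 | 8 |
|---|---|---|---|---|---|
| m/(m-1) | 2.00 | 1.50 | 1.33 | 1.20 | 1.14 |

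**Step 3: illustration by arm.** Assume that time on treatment is exponential with the illustrative PFS medians in SAP 5.2, and that cycles last 4 weeks (Protocol 7.2). Then m = 1/(1 - 2^(-4/median)). At 10 weeks, m = 1/(1 - 0.758) = 4.13; at 16 weeks, m = 1/(1 - 0.841) = 6.29. Take an equal true rate of 10% per cycle in both arms.

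| Medians B/A (weeks) | m, B/A | m/(m-1), B/A | Reported, B vs A | Ratio B/A |
|---|---|---|---|---|
| 10/16 | 4.13/6.29 | 1.32/1.19 | 13.2% vs 11.9% | 1.11 |
| 12/19.2 | 4.85/7.44 | 1.26/1.16 | 12.6% vs 11.6% | 1.09 |
| 16/25.6 | 6.29/9.74 | 1.19/1.11 | 11.9% vs 11.1% | 1.07 |

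**Step 4: reading 2, Cycle 1 removed from both parts.** With r1 the rate in Cycle 1 and r2 the rate later, the reported figure is r2 and the all-cycle rate is (r1 + (m-1)·r2)/m. The difference is (r2 - r1)/m, which is zero if r1 = r2. With the 10/16-week values:

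- r1 = 20%, r2 = 10%: -10/4.13 = -2.4 points in Arm B and -10/6.29 = -1.6 in Arm A.
- r1 = 5%, r2 = 10%: 5/4.13 = +1.2 points in Arm B and 5/6.29 = +0.8 in Arm A.

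**Step 5: effect of restoring Cycle 1.** If a share q of patients received only the first infusion, the denominator per patient goes from m-1 to m-q. With q assumed between 0 and 10%, it grows by a factor of 1.30 to 1.33 at m=4 (3.9/3 to 4/3) and 1.18 to 1.20 at m=6 (5.9/5 to 6/5). Under reading 1 the reported rates fall by the same factors.

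**The case against.** The strongest reply is that this is a footnote slip in descriptive tables, and that Cycle 1 is visible elsewhere. Much of that stands. The patient-level rows of Table 12.1.3.1.2 carry no Cycle 1 exclusion. Table 12.1.3.1.3 includes Cycle 1, the listings show each omission by cycle, and cumulative dose in SAP 8.2 runs from the first cycle to the last, so dose intensity reflects Cycle 1 omissions. A reader might infer that first exposure and one-cycle patients vanish from the report; they do not.

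A reader might also infer that the SAP plans to drop Cycle 1 for reductions. The susceptible-cycle row in Table 12.1.4.2 keeps it. The fault there is a conflicting reference, plausibly a copying error.

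Nor do the documents show that the rates must be numerically wrong. The numerator is undefined. If Cycle 1 is removed from both parts, the result is a valid rate for Cycle 2 onward under an incomplete label. The instruction in SAP 12.1.4 to consider all reductions, and the unrestricted listings, suggest that Cycle 1 events are counted, but do not settle it.

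Finally, the arm comparison rests on PFS medians standing in for treatment length. Protocol 5.2 also ends treatment for toxicity, refusal, long delay or repeated dose reduction, which could shorten Arm A treatment relative to its PFS. Shorter treatment in Arm B is plausible, and cycles after crossover are excluded, but it is an assumption.

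None of this removes the conflict between the omission footnote and SAP 8.2.

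**Conclusion.** The point holds in a limited form. The omission denominator in Table 12.1.3.1.2 is inconsistent with SAP 8.2, with Table 12.1.3.1.3 and with the days on which omissions are defined. Tables 12.1.4.2 and 12.1.4.3 have two conflicting denominators.

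The size and direction of any error are not fixed by the documents. With Cycle 1 events in the numerator, inflation runs from 2.00 at two cycles per patient to 1.14 at eight. Under the assumed treatment lengths and equal true 10% rates, the artificial gap between arms is 0.8 to 1.3 percentage points. With Cycle 1 out of both parts, the fault is an unlabelled restriction, with no numerical error if Cycle 1 and later rates are equal.

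A claim of bias between arms in the plitidepsin rates would go too far, since those rows do not apply to Arm B. Only the dexamethasone cycle-level percentages can be distorted between arms, and the SAP attaches no test or decision to them. Patient-level rows, listings, dose intensity and the primary PFS analysis are unaffected. The correction is worth making because the written rule yields either an inflated or a mislabelled rate.

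**What to change.** 1. In Table 12.1.3.1.2, define susceptible cycles separately for plitidepsin and dexamethasone: all cycles, Cycle 1 included, in which a dose after the first administration of Cycle 1 was due before treatment was permanently stopped. Do not use the on-treatment period of SAP 8.2 for this. It runs 30 days past the last dose and would count doses that were never due.
2. State that numerator and denominator use the same set of cycles.
3. In Tables 12.1.4.2 and 12.1.4.3, point the rate footnotes to the reduction-susceptible count that Table 12.1.4.2 already defines.
4. Keep the exclusion of the whole first cycle for the delay tables only.

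The cost is three corrected footnotes, one sentence on the numerator and the matching programming. No new data are needed.

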12.1.4 Dose reductions

All dose reductions should be considered and described, specifying the reason for reduction (hematological toxicity, non-hematological toxicity or other causes).

Listing 12.1.4.1.1 Dose reductions

Arm	Patient id.	Cycle	Day	Agent reduced	Cycle start date	Previous dose	Reduced dose	Reason for dose reduction	Dose reduction Spec.
...									

Results after crossover will be highlighted

Table 12.1.4.2 Number of patients and cycles with dose reduction, any relationship

	Arm A		Arm B		Total	
	N	%	N	%	N	%
No. of patients treated	X	XX.X	X	XX.X	X	XX.X
No. of patients with any dose reduced						
No. of patients with:			NA			
No plitidepsin reduction						
1 cycle with plitidepsin dose reduced						
2 cycles with plitidepsin dose reduced						
No. of patients with:						
No dexamethasone reduction						
1 cycle with dexamethasone dose reduced						
2 cycles with dexamethasone dose reduced						
No. of cycles administered						
No. of cycles susceptible to have any dose reduced*						
No. of cycles with plitidepsin dose reduced **			NA			
No. of cycles with dexamethasone dose reduced**						
No. of cycles with plitidepsin dose reduced (Treatment-related)			NA			
No. of cycles with dexamethasone dose reduced (Treatment-related)						

(*) All cycles excluding first cycle of those patients who have only received the first infusion. (**) Denominator= Number of cycles susceptible to have a dose omission

NA: Not applicable. Cycles after crossover will be excluded

Table 12.1.4.3 Number of patients and cycles with dose reduction according to the relationship

Reasons for reductions	Arm A		Arm B		Total	
	N	%	N	%	N	%
Plitidepsin						
No. of cycles with dose reductions*			NA			
Treatment-related	X	XX.X			X	XX.X
Hematological						
Non-hematological						
Both						
Non-treatment-related						
Dexamethasone						
No. of cycles with dose reductions*						
Treatment-related	X	XX.X	X	XX.X	X	XX.X
Hematological						
Non-hematological						
Both						
Non-treatment-related						

(*) Denominator= Number of cycles susceptible to have a dose omission. (**)Hematological reason, non-hematological reason or both.

NA: Not applicable. Cycles after crossover will be excluded

Listing 12.1.4.4 Dose reductions due to AEs

Arm	Patient id.	Cycle	Preferred term code	Adverse event reported (verbatim)	Grade	Relationship	Onset date	Resolved date	Significant consequences
...									

AEs with action = 'Dose reduced/adjusted' or 'Reduced and delayed'. Results after crossover will be highlighted

12.1.5 Infusions temporarily interrupted

A listing of the patients who had infusions temporarily interrupted with the corresponding reasons will be provided.

Listing 12.1.5.1 Interrupted Infusions listing.

Arm	Patient id.	Cycle	Infusion	Interrupted	Reason
...				Yes	

Results after crossover will be highlighted

12.1.6 Prophylactic medication administration

A listing of the patients who have not received Ondansetron, Diphenhydramine and Ranitidine or equivalents in the Arm A with the corresponding reasons will be reported.

Listing 12.1.6.1 Patients and cycles without prophylactic medication administration

Arm	Patient id.	Cycle	Infusion	Prophylactic medication not taken*	Reason
	...				

(*) Ondansetron, diphenhydramine or ranitidine.

12.2 Adverse Events (AEs)

12.2.1 Adverse events

As far as all the toxicities are concerned, the NCI-CTC grade will be used wherever an NCI-CTC grading exists. Otherwise, the severity will be noted. As a convention, the term «Grade» will always be used. Toxicities will be described according to the worst NCI-CTC grade or, for toxicities which do not form the subject of NCI-CTC classification, according to the worst severity.

In this section the adverse events will be described and different tables will be created for events related to treatment (stated as related to at least one of the two trial medications or unknown relationship). In case of a high frequency of adverse events attributable only to one of the investigational drugs, all tables in this section will be duplicated to show adverse events related to plitidepsin or dexamethasone (i.e. table 12.2.2.2, additional tables 12.2.2.2p and 12.2.2.2d).

Type of toxicity and worst grade or severity by cycle and by patient will be summarized according to the Preferred Term coded with MedDRA. Tables will be organized per category of events using System Organ Class of MedDRA.

